^a Pregnancy test (urine or blood) for female subjects of childbearing potential will be assessed per local laboratory.

^b TTP recurrence information includes presenting symptoms (assessed at recurrence visit), duration (assessed at the Week 1 visit) and outcome (assessed at the recurrence FU visit).

^c Heart rate and blood pressure to be assessed after 5 min in supine position.

^d To be assessed at the post-daily PE Day 29 only.

** Treatment with caplacizumab may not be initiated for subjects who do not fulfil the caplacizumab treatment criteria. These subjects will be treated with standard of care only. For the Schedule of Assessments, please refer to [Appendix 1](#).

-
- ^e Clinical laboratory analyses include hematology (Hb, Hct, RBC, WBC, platelets); chemistry (AST, ALT, LDH, creatinine, protein, cholesterol and CRP). Urinalysis includes assessment of albumin. The results of assessment of platelet count and LDH levels performed as per standard of care (by a local laboratory) at any time during the recurrence period will be collected in the eCRF, if available.
- ^f At the recurrence visit and the Treatment Day 3 visit, samples need to be collected prior to start of the PE treatment and/or study drug administration (whatever comes first). At all subsequent visits, blood samples need to be taken prior to study drug administration.
- ^g In case of a severe and/or serious hypersensitivity reaction, an additional blood sample to characterize the reaction should be collected as soon as possible after the start of the event.
- ^h PD parameters include RICO and vWF:Ag.

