2.1.3.1.2 Duration of the TTP recurrence

The duration of TTP recurrence in days (time to platelet count response) is defined as initial platelet count $\geq 150 \times 10^9/L$ with subsequent stop of daily PE within 5 days. The start and end date time of the recurrence, for the calculation of the duration of TTP recurrence, are captured in the eCRF. There will be no imputation of missing data.

2.1.3.1.3 Outcome of the TTP recurrence:

The outcome of the TTP recurrence is assessed at the recurrence follow-up visit and is collected in the eCRF.

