2.4.5.5.2 ADA and mADA analysis

ADA

Immunogenicity samples will be evaluated in a three-tiered homogenous bridging ADA assay (screen/confirmatory/titer tiers). All samples confirmed positive in the ADA assay will be titrated. The log₁₀ (titer) will be reported. The titer represents the last dilution factor of the sample's titration series still scoring positive in the ADA assay.

Samples scoring negative in the ADA assay are not titrated and the respective log₁₀ (titer) is reported as < log₁₀ (Minimal required dilution [MRD]) with MRD = 96, i.e. log₁₀ (titer) < 1.98. The latter are not included in descriptive statistics on titers.

Subjects will be classified as follows based on the ADA assay results:

1. ADA negative: no positive ADA samples at any of the sampling time points
2. ADA positive: positive ADA samples at one or more sampling time points
3. Inconclusive: no positive ADA samples and drug is present at levels higher than the drug tolerance characteristics of the assay. Drug tolerance limit is 10µg/mL.
4. Missing: missing will only be used if samples were taken but no reportable result could be obtained for that subject.

Based on these ADA results, no statement can be made on pre-existing antibody (pre-Ab) positivity pre-dose due the plasma exchange (PE) procedure. During PE (i) pre-Ab present in donor plasma can be transferred to the subject and/or (ii) pre-Ab might be diluted during PE treatment. PE is part of the standard of care and no ADA pre-PE sample will be available to determine the pre-Ab status of the subject.

mADA

All confirmed positive ADA samples will be further evaluated in a mADA assay. This assay employs a modified caplacizumab molecule as detection reagent in the bridging format, ie, caplacizumab-Ala variant. The modification constitutes of a single alanine extension at the C-terminus of caplacizumab. The mADA assay allows detection of drug-induced treatment-emergent (TE) ADA, whereas pre-Ab is not detected. In other words, drug-induced TE ADA will score positive in the mADA assay. All samples confirmed positive in the mADA assay will be titrated and reported as log₁₀ (titer). Samples scoring negative in the mADA assay are not titrated and the respective log₁₀ (titer) is reported as < log₁₀ ([MRD) with MRD = 96, ie, log₁₀ (titer) < 1.98. The latter are not included in descriptive statistics on titers.

Subjects will be classified as follows based on the mADA assay results:

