1. Pre-Ab positive - Drug-induced TE ADA negative: all ADA positive samples analyzed in the mADA assay score negative ⁽ⁱ⁾
2. Pre-Ab negative - Drug-induced TE ADA positive: all ADA positive samples analyzed in the mADA assay score positive ⁽ⁱⁱ⁾
3. Pre-Ab positive - Drug-induced TE ADA positive: from the ADA positive samples analyzed in the mADA assay, some score positive and some score negative ⁽ⁱⁱ⁾
4. Inconclusive: no positive ADA samples in the mADA assay and drug is present at levels higher than the drug tolerance characteristics of the assay. Drug tolerance limit is 10 µg/mL.
5. Missing: Relevant samples are missing.

(i) Pre-Ab can originate from the donor plasma introduced during PE procedure or can originate from the subject itself.

(ii) Subjects will be classified “pre-Ab negative- drug-induced TE ADA positive”, in case all ADA positive samples analyzed in the mADA assay are positive in the latter assay.

Overall subject classification

For the overall subject classification, subjects will be classified as follows based on the ADA and /or mADA assay results:

1. Pre-Ab negative - Drug-induced TE ADA negative: no positive ADA samples
2. Pre-Ab positive - Drug-induced TE ADA negative: all ADA positive samples analyzed in the mADA assay score negative

3. Pre-Ab negative - Drug-induced TE ADA positive: all ADA positive samples analyzed in the mADA assay are positive
4. Pre-Ab positive - Drug-induced TE ADA positive: from the ADA positive samples analyzed in the mADA assay, some are positive and some are negative
5. Inconclusive: no positive ADA samples or positive mADA samples and drug is present at levels higher than the drug tolerance characteristics of the assay. Drug tolerance limit is $10\mu\text{g/mL}$.
6. Missing: Relevant samples are missing.

Subjects classified “ADA negative” based on ADA assay results will per default be classified as “Pre-Ab negative- Drug-induced TE ADA negative” for the overall subject classification (#1). No results will be reported for samples not evaluated in the mADA assay (#6).

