2.4.5.5.3 NAb

The neutralizing antibody (NAb) assay is based on vWF-platelet interaction. As this assay is not sufficiently drug tolerant to detect NAb under treatment, only pre-dose samples (i.e. baseline visit), recurrence visit day 1 (if applicable) and wash out samples (follow-up samples) will be analyzed. All samples confirmed positive in the ADA assay at these time points will be analyzed in the NAb assay. Samples scoring negative in the NAb assay will be reported as $<\log_{10}(\text{MRD})$ with $\text{MRD} = 2.30$ i.e. $\log_{10}(\text{titer}) < 0.36$. The latter are not included in descriptive statistics on titers. Samples scoring positive will be reported as ≥ 0.36 . These positive samples should be plotted as $\log(\text{MRD})$ equal to 0.36 in the figure.

Subjects will be classified based on their pre-dose status (i.e. baseline visit) and treatment emergent (TE) status. Subject classification based on NAb is as follows:

1. Pre-dose negative,- TE negative: no NAb positive samples
2. Pre-dose negative,- TE positive: ADA or NAb negative at baseline visit and one or more NAb positive samples post-dose
3. Pre-dose positive,- TE negative: NAb positive at baseline visit and all post-dose samples score NAb negative
4. Pre-dose positive,- TE positive: NAb positive at baseline visit and at least 1 NAb positive post-dose sample
5. Missing: Relevant samples are missing.

Subjects with no positive ADA samples will be classified as NAb pre-dose negative, TE negative (data imputation). In listings, samples not evaluated in the NAb assay will be indicated as not analyzed (NA). In graphical presentations, these samples will be presented as negative results.

2.4.5.5.4 NECA (*neutralizing antibody epitope characterization assay; null variant assay; alternative NAb*): *ADA with neutralizing potential*

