To detect ADA with potential neutralizing activity under treatment, an alternative NAb assay will be used, consisting of the homogenous bridging ADA assay in which an altered caplacizumab molecule (i.e. caplacizumab with mutated complementary determining region [CDR] regions) is added in excess to capture all non-CDR binding ADA. Consequently, using this assay, only ADA binding to the CDRs of the Nanobody are detected. Those ADA are considered to have neutralizing potential, although clinical relevance (i.e., ability to block binding of von Willebrand factor [vWF]) will be dependent on affinity and titer level and should be related to PK, PD, safety and efficacy read-outs.

All samples confirmed positive in the ADA assay, will be analyzed in this alternative NAb assay. Samples scoring positive in the alternative NAb assay are titrated. The titer per sample is reported as log₁₀ (titer). Samples scoring negative in the alternative NAb assay are not titrated and the respective titer is reported as < log₁₀ (MRD) with MRD = 96, i.e. log₁₀ (titer) < 1.98. The latter are not included in descriptive statistics on titers.

Subjects will be classified based on their pre-dose status (i.e. baseline visit) and treatment emergent status. Subject classification based on alternative NAb assay is as follows:

1. Pre-dose negative, - TE negative: no alternative NAb positive samples
2. Pre-dose negative, - TE positive: ADA or alternative NAb negative at baseline visit and one or more alternative NAb positive samples post-dose.
3. Pre-dose positive, - TE negative: alternative NAb positive at baseline visit and no titer increase post-dose or all samples scoring alternative NAb negative post-dose
4. Pre-dose positive, - TE positive: alternative NAb positive at baseline visit and titer increase post-dose. If a positive pre-dose titer is reported, the titer is considered to be significantly increased post-dose, if the highest post-dose titer compared to the pre-dose titer is higher than the minimum significant ratio [MSR] value: the increase of the log₁₀ titer post versus pre-dose should be > log₁₀ (MSR). The MSR value was determined in Ablynx GLP and is 1.89.
5. Inconclusive: no alternative NAb positive samples and drug is present at levels higher than the drug tolerance characteristics of the assay. Drug tolerance limit is 10µg/mL.
6. Missing: Relevant samples are missing.

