Scatter plot of drug concentration (logarithmic) by subject category based on the ADA, mADA, NECA and Nab results. Connect means per group to visualize mean drug concentrations per subject category.

Scatter plot of % change from baseline vWF:Ag concentrations (logarithmic) by subject category based on the ADA, mADA, NECA and Nab results. Connect means per group to visualize mean % change from baseline vWF:Ag concentrations per subject category.

Scatter plot of RICO activity (logarithmic) by subject category based on the ADA, mADA, NECA and Nab results. Connect means per group to visualize mean RICO activity per subject category.

Km plot time to platelet count response by subject category based on the ADA, mADA, NECA and Nab results.

Subgroup analysis by hypersensitivity analysis (no or at least one hypersensitivity reaction) based on ADA/mADA results (overall subject classification) and based on NAb results

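### The Kaplan–Meier plot of platelet response by antibody category lets samples taken after the response decide which curve a subject is on

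*SAP*

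**What the plan says.** SAP 2.4.5.5.5 lists, among the immunogenicity displays, a "Km plot time to platelet count response by subject category based on the ADA, mADA, NECA and Nab results". SAP 2.4.5.5.2 to 2.4.5.5.4 define the categories:

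- **ADA:** "ADA positive: positive ADA samples at one or more sampling time points".
- **mADA:** pooled over the ADA-positive samples. The mixed class, for example, applies when "from the ADA positive samples analyzed in the mADA assay, some score positive and some score negative".
- **NECA (the alternative NAb assay):** "All samples confirmed positive in the ADA assay, will be analyzed in this alternative NAb assay". The treatment-emergent part compares post-dose results with the baseline visit.
- **NAb:** "only pre-dose samples (i.e. baseline visit), recurrence visit day 1 (if applicable) and wash out samples (follow-up samples) will be analyzed".

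None of these stops at the platelet response, and no landmark or time-dependent status is described. SAP 2.1.3.1.2 defines response as a first count of at least 150 × 10⁹/L "with subsequent stop of daily PE within 5 days".

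On plasma exchange (PE), SAP 2.4.5.5.2 says: "During PE (i) pre-Ab present in donor plasma can be transferred to the subject". The same sentence adds that PE may dilute such antibody.

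**The concern.** In a time-to-event comparison, the groups should be fixed by information available before the event. Here a subject who responds in the first days and first turns antibody-positive weeks later is drawn on a positive curve, although the antibody was not there when the platelets recovered.

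A second route runs backwards. Daily PE ends only after response, so a slower responder has more PE. By the SAP's own account, PE can change the ADA result by bringing in donor antibody or by diluting antibody. Speed of response can then influence the category instead of the reverse.

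Immunogenicity of (repeated) treatment is a main endpoint, and efficacy of repeated use is an objective. SAP 2.4.5.5.4 asks that ADA with neutralising potential be judged against efficacy as well as PK, PD and safety. This plot is the only group display in 2.4.5.5.5 that sets antibodies against platelet response, and readers will use it for that judgement.

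**Working it through.** The documents give no figure for this analysis (no sample size, event count or test), so there is nothing to reproduce. The checks are a count from the schedule and two illustrations under stated assumptions.

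**1. Samples after response in a treated episode.** Protocol Table 2 schedules ADA at the recurrence visit, treatment Day 3, post-daily-PE Days 1, 8, 15, 22 and 29, and the recurrence follow-up visit: 2 + 5 + 1 = 8. Response under SAP 2.1.3.1.2 comes before the stop of daily PE, so every post-PE sample in a responder comes after response.

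- No extension: 6/8 = 75%.
- Full four-week extension (four more weekly samples): 10/12 = 83%.
- If Day 3 also follows response: 7/8 = 88% to 11/12 = 92%. The phase II TTP study (protocol 1.2.4) had a median of 2.97 days on caplacizumab. With an assumed exponential time to response, 1 − 0.5^(2/2.97) = 37% would respond within two days.

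The count uses the response definition in 2.1.3.1.2. SAP 2.1.3.2.1 defines a simpler time to a count of at least 150 without the PE condition. On that definition a first qualifying count could fall after daily PE has stopped.

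**2. If twice-yearly samples also counted.** The SAP does not say. Seven scheduled baseline and six-monthly samples would make 15 in all (one episode, no extension, no visit cancelled). For a recurrence in months 1 to 3, (6 + 6)/15 = 80% follow response. At month 31, (6 + 1)/15 = 47%.

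**3. Attenuation by later positives.** Assume exponential times and a true response-rate ratio of 0.50 for antibody present at the recurrence visit. Let a be the proportion positive at that visit and b the proportion of the others who turn positive later. Among ever-positives, the share truly positive at the visit is f = a / [a + (1 − a)b]. Mean time in ever-positives is (1 + f) times that in negatives, so the plotted ratio is 1/(1 + f).

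| a | b | f | plotted ratio |
|---|---|---|---|
| 5% | 5% | 0.0500/0.0975 = 0.513 | 0.66 |
| 10% | 10% | 0.100/0.190 = 0.526 | 0.66 |
| 5% | 20% | 0.050/0.240 = 0.208 | 0.83 |

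Grouping by recurrence-visit status has f = 1 and returns 0.50. The values of a and b are assumptions.

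**4. PE transfer with no antibody effect.** A simulation of 400,000 subjects took exponential response with median 2.97 days, PE days = ceiling(T) + 2, and an assumed chance p per PE day of becoming ADA-positive from donor plasma.

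- p = 0.5%: median 5.35 days in positives against 2.90 in negatives; rate ratio 0.62.
- p = 5%: 4.89 against 2.44 days; rate ratio 0.56.
- A category fixed before PE gave 1.00.

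The model is rough: mean PE was 6.8 days against 5.9 in the phase II caplacizumab arm. It covers transfer only; dilution of antibody would push the other way.

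**5. Is a pre-exchange sample available?** Protocol Table 2, footnote f: "At the recurrence visit and the Treatment Day 3 visit, samples need to be collected prior to start of the PE treatment" or study drug, whichever is first. SAP Table 5, footnote f, agrees, and Table 6, footnote d, requires the same before the first PE in untreated episodes. SAP 2.4.5.5.2 states that no such ADA sample will exist. The protocol also allows up to one PE before caplacizumab starts. These statements conflict.

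**The case against.** The strongest reply is that this is one descriptive figure in a study with no formal tests (SAP 2.4.4.8). The SAP also plans incidence by visit, titre-over-time plots, individual profiles with PE days marked, and listings, so the timing of each positive result is visible. That lowers the stakes. It does not repair the grouping, because the individual profiles do not carry platelet counts.

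Second, the PE route does not act equally on every assay. The SAP says the mADA assay does not detect pre-existing antibody, so donor antibody should not create a drug-induced positive. This stands. Donor antibody can still put a subject in a pre-Ab-positive class, as the SAP's own note to the mADA classification says. The timing problem also remains for mADA.

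Third, the NAb and NECA classes separate subjects by baseline-visit status. This helps in part, but each group is split again by what happens after dosing, and baseline may precede a recurrence by a long interval.

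Fourth, the SAP analyses recurrence data separately from six-monthly data, so a per-episode category is a fair reading. This is accepted, and the count of 6 in 8 already assumes it.

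**Conclusion.** The point holds. As written, the plot groups subjects partly by results obtained after the outcome. In a treated responder without extension, 75% of scheduled ADA samples follow the response, which rests on the definition in SAP 2.1.3.1.2 and the protocol schedule. The rate ratios above show what such grouping can do under assumed antibody frequencies; they do not estimate the bias in this trial.

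A reader might infer more than the documents support:

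- **That the category is a whole-study class fed by all samples, most of them after response.** The SAP does not say whether six-monthly samples count. If they did, the share for a late recurrence falls to 47%. NAb uses selected visits only, and an untreated episode has a single ADA sample, scheduled before PE.
- **That positives will look falsely slow.** The SAP names both transfer and dilution, so the direction of the PE effect is not known.
- **That the immunogenicity endpoint or an error rate is compromised.** Incidence tables are unaffected and nothing is tested. The consequence is a figure that may mislead.
- **That the drug-concentration, RICO and vWF:Ag plots by category fail in the same way.** Those measurements run throughout the sampling schedule, so the ordering argument does not carry over as it stands, and no such claim is made.

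**What to change.** In SAP 2.4.5.5.5, for this plot only, group each episode by ADA, mADA, NECA and NAb status in that episode's recurrence-visit sample. All four assays already cover that visit, with the last three run on ADA-positive samples. Keep the ever-positive and treatment-emergent categories for the incidence tables, and state whether they are built per episode or over the whole study.

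Reconcile SAP 2.4.5.5.2 on the absence of an ADA sample before PE with Protocol Table 2, footnote f, and SAP Tables 5 and 6. Flag episodes whose recurrence-visit sample was in fact taken after PE. For those, use the last baseline or six-monthly sample before the episode, which that episode's PE cannot have altered.

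The cost is SAP wording and one re-derived grouping variable, with no new sampling if the scheduled samples were taken. The drawback is fewer positives, and so a less precise curve for that group.

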2.4.6 Analyses of pharmacokinetic and pharmacodynamic variables

2.4.6.1 Analysis of pharmacokinetic

Determination of caplacizumab concentrations in plasma will be done by a validated enzyme-linked immunosorbent assay (ELISA)-based method according to the bioanalytical methodology and procedures described in a separate Bioanalytical Analysis Plan.

Individual study drug concentrations will be listed. In addition, a listing of the actual sampling times relative to the study drug administration times will be presented. Drug concentrations will be summarized by analysis period and scheduled sampling time using descriptive statistics and will be listed and summarized in tabular and graphical form.

Spaghetti plot of individual drug concentrations over time will be provided. Nominal sampling times are used. Plots will be created with both linear and semi-logarithmic PK profiles.

Line plot of the mean drug concentrations vs. scheduled sampling time, including SE bars, will be provided for all participants from the recurrence visit up to recurrence follow-up visit or study completion/discontinuation (if earlier). Plots will be created with both linear and semi-logarithmic PK profiles.

Line plot of the geometric mean drug concentrations vs. scheduled sampling time, including geometric SD bars, will also be provided for all participants from start of the study up to recurrence of aTTP or study completion/discontinuation (if earlier). Plots will be created with both linear and semi-logarithmic PK profiles.

All analyses will be run on patients treated with the IMP in the recurrence population.

Pharmacokinetic concentrations and descriptive statistics will be reported to 3 significant digits for values up to, but not including 1000. Values equal to and above 1000 will be reported as the value without decimal signs.

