3.4.5. PHARMACOKINETIC ASSESSMENTS

3.4.5.1. SAMPLE COLLECTION AND HANDLING

In case of a recurrence, blood samples of approximately 2.0 mL will be taken for analysis of caplacizumab concentrations⁺⁺⁺, at the time points defined in the [Schedules of Assessments](#).

The blood samples will be collected via an indwelling i.v. catheter or by direct venipuncture. For further details on sample collection, shipment, storage and processing, please refer to a separate Lab Manual.

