3.4.6. PHARMACODYNAMIC ASSESSMENTS

3.4.6.1. SAMPLE COLLECTION AND HANDLING

Throughout the study, blood samples of approximately 3.5 mL will be taken for analysis of vWF:Ag levels, according to the time points defined in the [Schedules of Assessments](#).

In case of a recurrence, an additional blood sample of approximately 3.5 mL will be taken for analysis of RICO⁺⁺⁺, at the time points defined in the [Schedules of Assessments](#).

⁺⁺⁺ PK and RICO will not be assessed if treatment with caplacizumab has not been initiated.

All PD blood samples will be taken via an indwelling i.v. catheter or by direct venipuncture. For further details on sample collection, shipment, storage and processing, please refer to a separate Lab Manual.

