2.4.6.2 Analysis of Pharmacodynamics

RICO activity and vWF:Ag concentration will be summarized using descriptive statistics by analysis period and will be listed and summarized in tabular and graphical form.

RICO activity will also be categorized and represented as frequency tabulation (number of participants and percentages) by analysis period and timepoint using following categories: <20% / ≥20%.

Line plots (Mean ±SE) of RICO activity and vWF:Ag concentrations vs. time points for all participants from start of the study up to recurrence of aTTP or study completion/discontinuation (if earlier) will be provided.

Analyses of RICO activity will be run on the patients treated with IMP in the recurrence population. Analyses of vWF:Ag concentration will be run on the ITO and recurrence population. Pharmacodynamic concentrations or activity and their descriptive statistics will be reported to 3 significant digits.

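### The geometric-mean PK plot and the RICO and vWF:Ag line plots stop at recurrence, which is where dosing and PK/RICO sampling begin, so they show no on-drug data for a first recurrence

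*SAP*

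**What the plan says.** SAP 2.4.6.1 plans two mean line plots of drug concentration. The arithmetic-mean plot runs "from the recurrence visit up to recurrence follow-up visit or study completion/discontinuation (if earlier"). The geometric-mean plot, described in the next paragraph, "will also be provided for all participants from start of the study up to recurrence of aTTP or study completion/discontinuation (if earlier"). The section then limits its scope: "All analyses will be run on patients treated with the IMP in the recurrence population".

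SAP 2.4.6.2 plans mean line plots of RICO and vWF:Ag "vs. time points for all participants from start of the study up to recurrence of aTTP or study completion/discontinuation (if earlier) will be provided". It adds: "Analyses of RICO activity will be run on the patients treated with IMP in the recurrence population". vWF:Ag is analysed in both the ITO and the recurrence populations.

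On sampling, Protocol 3.4.5.1 says "In case of a recurrence, blood samples of approximately 2.0 mL will be taken for analysis of caplacizumab concentrations", and 3.4.6.1 says "In case of a recurrence, an additional blood sample of approximately 3.5 mL will be taken for analysis of RICO". SAP 2.1.5 and 2.1.6 define the PK variable, and RICO, only for patients treated with study drug. vWF:Ag is sampled throughout the study.

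**The concern.** Two mean plots of the same concentrations, in the same section and population, are given different windows: one starts at the recurrence visit and the other stops at recurrence. No reason is given. The RICO and vWF:Ag plots take the second window. Because treatment in this study starts at recurrence, a plot that stops there cannot describe exposure or drug effect.

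Evaluating the safety and efficacy of repeated use is a stated objective, and RICO and vWF:Ag are the study's PD measures. SAP 2.4 also specifies how geometric-mean PK graphs are to be drawn (with a geometric SD flag), so that figure is an intended output. If the windows stay as written, programmers must either produce uninformative figures or depart from the SAP without documentation.

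**Working it through.** The plan states no figure to reproduce. The check sets the plot window against the dosing rule and the sampling schedules.

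**1. When drug is given.** Protocol 3.3.1 starts open-label caplacizumab at a recurrence. No dosing is planned between enrolment and recurrence.

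**2. Scheduled samples from study start until recurrence** (Protocol Table 1, SAP Table 4). The six-monthly schedule has 7 visits (baseline, 6, 12, 18, 24, 30 and 36 months). It has no PK row, and vWF:Ag is its only PD parameter.

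- PK: 0
- RICO: 0
- vWF:Ag: up to 7, all off drug

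**3. Scheduled samples in a treated episode** (Protocol Table 2, SAP Table 5). PK, RICO and vWF:Ag are taken at every visit.

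- Without extension: recurrence visit, Day 3, post-daily PE Days 1, 8, 15, 22 and 29, follow-up visit = 8 visits.
- With full extension, reading the open-ended weekly visits in Protocol Table 2 as adding Days 36, 43, 50 and 57: 8 + 4 = 12 visits. This is a maximum; SAP Table 5 lists weekly visits only to Day 29.
- Visits after the first dose: 8 − 1 = 7, or 12 − 1 = 11.
- Of these, the number before the recurrence that opened the episode: 0 of 7, or 0 of 11.

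**4. The boundary sample.** If the window includes the recurrence visit, it gains one sample of each analyte. The footnote to both recurrence schedules requires that sample before PE or study drug, whichever comes first, so for a first recurrence it is pre-dose.

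- *PK.* The value is expected to be below quantification. SAP 2.5.1 treats such values as missing and reports no statistics at a time point where they exceed one third of the total.
- *RICO.* The below-quantification rule is written for PK concentrations, so this value can be plotted. It is a baseline (SAP 2.1.1 names it as one), with nothing after it.

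**5. Could drug left over from C301 supply exposure data?** The documents give no human half-life. As an assumption I use the range across animal species in Protocol 1.2.3, 5 to 36 hours, and the 4-week C301 follow-up (28 × 24 = 672 h). Fraction remaining = 0.5^(672 / half-life).

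- 36 h: 672 / 36 = 18.7 half-lives; about 2.4 × 10⁻⁶ remains.
- 5 h: 672 / 5 = 134.4 half-lives; effectively nothing remains.

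Carry-over would not fill the plot anywhere in that range.

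**6. With the arithmetic-mean plot's window instead**, each treated episode without extension supplies 8 scheduled time points per analyte, 7 of them after the first dose.

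**The case against.** The strongest objection is that little is lost. Concentrations are summarised by analysis period and sampling time, with geometric mean and geometric SD (SAP 2.4, 2.4.6.1). Spaghetti plots and a correctly windowed arithmetic-mean plot are planned. RICO and vWF:Ag are summarised by analysis period in tables and graphs, and RICO is tabulated as below 20% or at least 20%. SAP 2.4.5.5.5 adds individual plots and scatter plots with connected means by antibody category. This stands and sets the size of the point. A reader might infer that the study would have no on-drug exposure or PD evidence; the documents do not support that. They do not rescue the specified windows either: no other geometric-mean PK plot, and no overall mean line plot of RICO or vWF:Ag with an on-drug window, is named.

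A reader might also infer that the RICO figure would be empty. It could carry one pre-dose point, so the exact statement is that it holds no on-treatment data.

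Nor is the vWF:Ag window an error in the ITO population. vWF:Ag is measured at every six-monthly visit, and following subjects up to recurrence fits the group-wise definitions in Protocol 3.6.4 and SAP 2.4.4. The window fails only for the recurrence population.

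Last, the SAP does not say which recurrence closes the window. If a later one does, subjects with two or more recurrences would contribute on-drug samples from earlier episodes. That is why the conclusion is stated for a first recurrence. A subject with a single recurrence contributes no on-drug data on either reading.

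**Conclusion.** The point holds, with limited reach. Followed as written, the geometric-mean PK plot shows no exposure data for a first recurrence, the RICO line plot at most one pre-dose point, and the vWF:Ag line plot only off-drug levels. None of the 7 scheduled post-first-dose visits of an unextended episode (11 if fully extended) is plotted. What is lost is an on-drug geometric-mean PK figure and on-drug mean line plots of RICO and vWF:Ag. All analyses here are descriptive, and no endpoint, estimate or error rate changes.

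This assumes that the window closes at the first recurrence and that pre-dose concentrations there are below quantification. The RICO and vWF:Ag conclusions do not depend on the second assumption. The correction is worth making because a specified window cannot yield its intended output and a workable one already stands in the same section.

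**What to change.** For episodes treated with study drug, redefine the window of the geometric-mean PK plot (SAP 2.4.6.1) and the RICO line plot (SAP 2.4.6.2). It should open at the episode's recurrence visit and close at that episode's follow-up visit, or at the next recurrence visit or study completion/discontinuation if either comes first. Present the plots by recurrence episode. This matches the arithmetic-mean PK plot.

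For vWF:Ag, keep the plot from study start to recurrence in the ITO population and use the recurrence-period window in the recurrence population. A separate vWF:Ag plot for episodes not treated with study drug is optional, since those have only two sampling visits (Protocol Appendix 1, SAP Table 6).

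The cost is a wording change in two SAP subsections and the matching figure specifications. The samples are already in the schedule.
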